11.2 Correlative studies

Patients will have tumor samples analyzed for genomic alterations via 12-245 IMPACT targeted sequencing platform.

Additionally, ctDNA will be collected serially according to Table 11-1 to evaluate tumor clonal evolution. See lab manual for collection instructions.

MRD assessment via IS MRD assay will be performed using serial peripheral blood draws according to the schedule in Table 11-1. See lab manual for collection and shipping instructions.

Serial peripheral blood samples for PBMCs according to schedule in Table 11-1 will be obtained for 1) T-cell and NK-cell profiling and 2) CITE-Seq. See lab manual for collection instructions.

An optional pair of biopsies of involved peripheral nodal tissue at baseline and during cycle 1 between days 22-28 will be obtained to assess effect of therapy on the tumor microenvironment. See lab manual for collection instructions.

12.0 CRITERIA FOR REMOVAL FROM STUDY

Patients may voluntarily withdraw from the study or be removed from the study at the discretion of the investigator at any time. Patients may be withdrawn from the study if any of the following occur:

- Disease progression
- Ineligibility (at the cycle 1 day 1 evaluation or earlier) as defined in the inclusion/exclusion criteria
- Treatment will be discontinued at the request of the patient, refusal of therapy, non-compliance, or upon development of an intercurrent significant medical illness
- Significant protocol violation
- Unacceptable toxicity necessitating drug discontinuation as outlined in 10.5
- Decision by the investigator that termination is in the patient's best medical interest
- Loss to follow-up
- Development of active HBV, HCV, or HIV infection
- Pregnancy or positive pregnancy test
- Death of the patient
- Start of any other antineoplastic therapy

13.0 CRITERIA FOR OUTCOME ASSESSMENT AND ENDPOINT EVALUABILITY

13.1 Criteria for Therapeutic Response/Outcome Assessment

Response and progression of disease will be evaluated using the Lugano criteria (Figure 3).^{1,2} Clinical evaluation and tumor assessments will be performed periodically as indicated in Table 11-1. Clinical suspicion of disease progression at any time will require physical

examination and radiological confirmation to be performed promptly, rather than waiting for the next scheduled tumor assessment. In case of an unscheduled or delayed tumor assessment for any reason, subsequent tumor assessments must be performed according to the originally planned schedule.

13.2 Criteria for Study Endpoint Evaluability

All patients who received at least one dose of tafasitamab and one dose of lenalidomide will be considered evaluable for the primary endpoint of ORR and all secondary endpoints. This will be the primary analysis. Safety endpoints will be evaluated in all patients who received at least one dose of tafasitamab or one dose of lenalidomide. Any patient that is removed from the study for reasons other than progression will be counted as a failure for ORR analysis and as an event for PFS analysis (as long as they have received at least 1 dose of tafasitamab and 1 dose of lenalidomide). For OS analysis, patients who are removed from the study for any reason other than death will be censored at the time of study removal. The study will continue enrollment until the required number of evaluable patients (those that receive at least one dose of both study drugs) is reached in each stage of the study.

The primary and secondary endpoints will also be evaluated in the per-protocol cohort (patients who did not have any major protocol violations) as a supportive, secondary analysis.

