4.0 OVERVIEW OF STUDY DESIGN/INTERVENTION

4.1 Design

A single-center, single-arm, open-label phase II study evaluating the combination of tafasitamab and lenalidomide for treatment of adults with R/R MCL who have previously failed or could not tolerate BTKi therapy. Patients will be eligible if they have received one or more prior lines of therapy, one of which must have been a BTKi. Patients will be enrolled according to a Simon two-stage design, described in 14.0, with early stop criteria for lack of efficacy.

Tafasitamab will be administered intravenously and lenalidomide will be self-administered orally according to the treatment schema in 4.2. The primary endpoint is ORR (CR plus PR)

[figure not shown]

evaluated by PET/CT according to Lugano criteria at the end of cycle 12 or treatment discontinuation, whichever is earlier.^{1,2}

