4.2 Intervention

Patients will receive treatment with intravenous tafasitamab and oral lenalidomide for up to 12 cycles. Each cycle is 28 days in length. Lenalidomide will be self-administered at a dose of 20mg daily days 1-21 of cycles 1 through 12. During the first cycle, tafasitamab will be administered on days 1, 4, 8, 15, and 22. During cycles 2 and 3, tafasitamab will be administered weekly on days 1, 8, 15, and 22. During cycles 4 through 12, tafasitamab will be administered every other week on days 1 and 15. Upon earliest of completion of cycle 12 or EOT, patients will undergo radiologic evaluation of response. Patients who achieve SD, PR, or CR at completion of cycle 12 will continue tafasitamab maintenance therapy on day 1 of each cycle until the earliest of POD or 36 cycles (inclusive of the first 12 cycles).

Figure 1: Treatment schema

*One cycle = 28 days

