14.0 BIOSTATISTICS

Objectives:

The primary objective is to estimate the ORR, defined as the percent of patients (relative to the total number considered evaluable as in 13.2) who achieve CR or PR. The primary endpoint will be analysed when all patients have completed 12 cycles of treatment or at treatment discontinuation, whichever comes first.

Secondary objectives are estimates of OCR, DOR, PFS, OS, and TTP, and descriptions of incidence and severity of AEs. Exploratory objectives include rate of conversion to undetectable MRD, ctDNA/clonal evolution, antitumor immune response, and effects on tumor microenvironment immunosuppression.

Exploratory objectives are described in Section 3.1 Correlative studies.

Study design:

The primary endpoint is ORR and the study is designed to determine preliminary clinical effectiveness of tafasitamab and lenalidomide. Based upon limited data available for lenalidomide and associated combinations in the post-BTKi setting, the combination of tafasitamab and lenalidomide will be considered worthy of further evaluation if the ORR is greater than 30%. This combination will be considered promising in the R/R setting if the ORR is greater than 50% given multiple evolving treatment options for patients post-BTKi failure or intolerance. To this end, , a single-arm Simon's two-stage minimax design will

utilize a null (non-promising) ORR of 30% and an alternative (promising) ORR of 50%. In the first stage, a total of 19 patients will accrue. If 6 or fewer have objective response, the trial will close due to a lack of efficacy; otherwise, an additional 20 patients will accrue. If at the end of the study, 17 or more out of 39 have an objective response, the trial will be considered promising for future development. This design will give 80% power with a type I error rate of 5%. Patients will continue to enroll without holding enrollment while the interim analysis is evaluated in the first 19 patients.

The anticipated accrual rate for this study is 1 to 2 patients per month. We anticipate total accrual will be completed in 2-3 years. The study will continue enrollment until the required number of evaluable patients (those that receive at least one dose of both study drugs) is reached in each stage of the study.

Methods:

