Primary objectives: ORR will be calculated as a proportion and summarized along with 95% confidence intervals. Patients who withdraw prior to response evaluation will be classified as nonresponders for the primary objective.

Secondary objectives: OCR will be defined as the percent of patients who achieve CR, PR or stable disease (SD) at the time of ORR assessment. Patients who withdraw prior to response evaluation will be classified as failures. The OCR will be estimated by proportion along with 95% confidence intervals. DOR will be defined as the time from achievement of PR or CR to progression of disease (POD) according to Lugano criteria or death. PFS will be defined as the time from initiation of study treatment to the earlier of POD or death from any cause. OS will be defined as the time from initiation of treatment to death from any cause. Kaplan-Meier estimates of DOR, PFS, and OS will be calculated and presented with 95% confidence intervals. TTP will be defined as the time from start of treatment to POD or death specially from MCL, and will be estimated with 95% confidence intervals by cumulative incidence function. Death from other causes will be treated as a competing risk. Frequency and severity of adverse events will be summarized descriptively.

Exploratory objectives will be performed in conjunction with collaborating laboratories at MSK. Study designs and analytic approaches are detailed in Section 3.1. Most objectives will be summarized descriptively. For assessing association between minimal MRD and PFS, the log rank test will be used and Kaplan-Meier curves will be presented. For assessing association between genomic alterations discovered through MSK-IMPACT sequencing and time-to-event outcomes PFS and OS, Cox regression will be used and hazard ratios with 95% confidence intervals will be presented. For assessing association between genomic alterations and ORR, Fisher's exact test will be used, and p-values will be adjusted for multiple testing with the false discovery rate (FDR).

14.1 Populations for analysis include the following:

- Primary analysis (primary endpoint and all secondary endpoints): All patients who received at least one dose of tafasitamab and one dose of lenalidomide
- Safety analysis: All patients who received at least one dose of tafasitamab or one dose of lenalidomide

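### Section 13.2 counts a recorded responder who is later removed without progression as an ORR failure and a PFS event, whereas Sections 14, 4.1 and 2.2.3 do not, and no rule of precedence is given

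*Combined protocol and SAP*

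**What the plan says.** **ORR in Section 13.2.** For patients who received at least one dose of each drug: "Any patient that is removed from the study for reasons other than progression will be counted as a failure for ORR analysis". The sentence goes on "and as an event for PFS analysis".

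**ORR in Section 14 (Methods).** "Patients who withdraw prior to response evaluation will be classified as nonresponders for the primary objective". Here the timing of withdrawal relative to the evaluation decides the classification.

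**When response is evaluated.** Section 4.1 defines the primary endpoint as ORR "evaluated by PET/CT according to Lugano criteria at the end of cycle 12 or treatment discontinuation, whichever is earlier". Section 4.2 agrees: "Upon earliest of completion of cycle 12 or EOT, patients will undergo radiologic evaluation of response". Early discontinuation is thus an assessment point, not an automatic failure.

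**What follows the evaluation.** Section 4.2: "Patients who achieve SD, PR, or CR at completion of cycle 12 will continue tafasitamab maintenance therapy on day 1 of each cycle", up to cycle 36. Section 14 on the timing of the analysis: "The primary endpoint will be analysed when all patients have completed 12 cycles of treatment or at treatment discontinuation, whichever comes first".

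**Decision rules (Section 14).** The trial closes if 6 or fewer of the first 19 respond. "If at the end of the study, 17 or more out of 39 have an objective response", the treatment is called promising.

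**PFS.** Sections 2.2.3 and 14 both define it as time from start of treatment to progression or death from any cause. Neither mentions removal.

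**Removal.** Section 12 lists requested treatment discontinuation and toxicity that stops the drug among the reasons for which a patient may be withdrawn. Section 10.4 gives patients who stop both drugs an EOT visit and then follow-up about every 6 months.

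**The concern.** Two sections can classify the same patient differently on the primary endpoint.

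The clear case is a patient in CR or PR at the end of cycle 12 who enters maintenance and is then removed for toxicity or at their own request. This patient is a responder under 4.1 and 14 and a failure under 13.2. The case can arise in practice. Accrual is expected to take 2 to 3 years and the analysis waits for the last patient to reach cycle 12 or stop, so early responders may be well into maintenance, or already removed, by then.

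The less clear case is a patient who stops before cycle 12 with a CR or PR on the discontinuation scan. The rules diverge here only if the treatment stop is recorded as removal from the study, which Sections 12 and 10.4 leave open.

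For PFS, 13.2 makes the removal itself an event. The curve would in effect show time to treatment failure under a definition that says progression or death.

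With no stated precedence, an analyst could choose the rule after seeing which patients it affects.

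Three groups are not affected: patients removed before any response evaluation (nonresponders under both sections), deaths as PFS events, and patients who stop one drug only (Section 10.5.7 continues the other).

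**Working it through.** **1. Does the text rank the rules?** Sections 2.1 and 14 refer to patients evaluable as in 13.2, but that reference sets the denominator. In 13.2 the remark that this is the primary analysis follows the sentence on the population, not the removal rule. No other sentence gives precedence.

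**2. Reproduce the plan's design.** Inputs from Section 14: n1 = 19, stop if X1 ≤ 6; n2 = 20; promising if X1 + X2 ≥ 17; ORR 0.30 (null) and 0.50 (alternative).

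P(promising | p) = Σ over x = 7 to 19 of P(X1 = x) × P(X2 ≥ 17 − x), with X1 ~ Bin(19, p) and X2 ~ Bin(20, p).

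- p = 0.50: power 0.8036; stage 1 stop 0.0835.
- p = 0.30: type I error 0.0455; stage 1 stop 0.666.

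The stated 80% power and 5% ceiling reproduce, so the sample size is not in question.

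**3. Apply 13.2 literally.** Let f be the share of true responders reclassified by the final analysis. The documents give no removal rate, so f is an assumption. At a true ORR of 50%, 0.50 × 39 = 19.5 patients respond; f = 5%, 10% or 20% is then about 1, 2 or 4 patients. In scenario (i) the countable ORR is 0.50 × (1 − f) = 0.475, 0.45 or 0.40.

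| Scenario (true ORR 50%) | Quantity | f = 5% | f = 10% | f = 20% |
|---|---|---|---|---|
| (i) Equal in both stages | Power | 0.710 | 0.599 | 0.356 |
| | Stage 1 stop | 0.122 | 0.173 | 0.308 |
| (ii) f/2 of the first 19 at the interim, f of all 39 at the end | Power | 0.717 | 0.610 | 0.370 |
| | Stage 1 stop | 0.102 | 0.122 | 0.173 |
| (iii) None at the interim, f of all 39 at the end | Power | 0.722 | 0.618 | 0.377 |
| | Stage 1 stop | 0.084 | 0.084 | 0.084 |

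The power loss hardly depends on timing; the effect on the stage 1 stop does.

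Type I error at a true ORR of 30% is 0.029, 0.017 and 0.005 in (i), and 0.029, 0.018 and 0.005 in (iii).

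**4. Without an assumed rate.** If exactly k responders are reclassified after the interim, power = P(X1 ≥ 7 and total ≥ 17 + k):

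| k | 1 | 2 | 3 | 4 |
|---|---|---|---|---|
| Power at 50% | 0.722 | 0.617 | 0.497 | 0.373 |

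One such patient reverses the conclusion whenever exactly 17 of 39 respond. P(X1 ≥ 7 and total = 17) = 0.081 at 50%. For example, 19 recorded responders pass, but three later removals leave 19 − 3 = 16, which fails. At stage 1, 7 of 19 continues, while one removal leaves 6 and closes the trial.

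**5. PFS.** With 39 patients and no administrative censoring before the time point, each removal without progression or death lowers the event-free proportion at a later time by at most 1/39 = 2.6 percentage points. The reduction is 0 if that patient would have progressed or died by then anyway.

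**The case against.** The best defence is that the two ORR rules can be read together. Section 13.2 concerns evaluability: it keeps dosed patients who leave in the denominator as failures, and Section 14 supplies the timing. The literal reading also gives an odd result, since a responder later removed for progression stays a responder while one removed for toxicity does not. This suggests the sentence was aimed at patients who leave unevaluated. That may well be the intent, but the text does not say so. Section 14 states its timing limit for both ORR and disease control; 13.2 states none, and one clause there governs ORR and PFS together.

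Second, few patients may be affected. The 5% to 20% shares have no source in the documents, and Section 10.4's continued follow-up suggests that stopping drug need not be removal. Both points stand, and they limit the size of the effect rather than the conflict. It also stands that the literal rule is conservative, and that power remains 0.80 if the 30% and 50% hypotheses were meant as ORR counted under 13.2.

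Third, for PFS, 13.2 is the only rule for patients removed without an event and could be a deliberate convention. If so, it contradicts the definition in 2.2.3 and 14 and should carry its own name. The warning that censoring at removal may be informative is fair and is taken up in the fix.

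Finally, Sections 2.1 and 14 speak of achieving CR or PR without a time point, so tying ORR to the 4.1 evaluation says more than those sections do. It does follow the time point that 4.1 already sets, and the amendment should say this openly.

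**Conclusion.** The concern holds. As written, 13.2 reclassifies recorded responders as failures in the count that decides both stages, and it contradicts the plan's own PFS definition. The contradiction needs no assumed rate.

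Its size does. Taking the 30% and 50% hypotheses as response as assessed, power at 50% falls from 0.80 to between 0.71 and 0.72 if 5% of responders are affected, to between 0.60 and 0.62 at 10%, and to between 0.36 and 0.38 at 20%. The chance of a wrong stage 1 stop ranges from unchanged (0.08) to 0.31, depending on when removals occur. Type I error does not rise above 0.0455.

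This must be fixed because it touches the primary endpoint. The PFS point alone would be one that should be fixed. Confidence is high.

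**What to change.** 1. **ORR.** Amend 13.2 to agree with 14 and 4.1: a CR or PR documented at the protocol evaluation (end of cycle 12 or treatment discontinuation, whichever is earlier) counts as a response whatever the reason for later removal. Patients removed without a response evaluation are nonresponders.
2. **Removal.** State for the analysis whether stopping both drugs is recorded as removal from the study, and reconcile Section 12 with 10.4.
3. **PFS.** In the primary analysis count only progression or death as events, use the follow-up data collected under 10.4, and censor event-free patients at their last adequate disease assessment. Keep removal as event as a sensitivity analysis labelled time to treatment failure.

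**Cost.** Items 1 and 2 are wording only, since the evaluation at cycle 12 or EOT is already planned. Item 3 is wording plus a real downside. After treatment, 10.4 collects relapse information only about every 6 months, by telephone, records and/or visits, and its disease status updates name only patients who go on to maintenance. Assessment after removal is therefore less regular and censoring may be informative. The retained sensitivity analysis shows how much that matters. All three changes should be made before the response data are analysed.

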2.2 Secondary objectives

- 2.2.1** To determine disease control rate (DCR), defined as the percent of patients (relative to the total number evaluable) who achieve CR, PR, or stable disease (SD) at the time of ORR assessment.
- 2.2.2** To estimate DOR, defined as the time from achievement of PR or CR to progression of disease (POD) according to Lugano criteria.^{1,2}
- 2.2.3** To estimate PFS, defined as the time from initiation of study treatment to the earlier of POD or death from any cause.
- 2.2.4** To estimate OS, defined as the time from initiation of study treatment to death from any cause.
- 2.2.5** To estimate TTP, defined as the time from initiation of study treatment to POD or death from MCL.
- 2.2.6** To describe the safety of the combination of tafasitamab and lenalidomide in patients with R/R MCL, defined as the incidence and severity (according to National Cancer Institute Common Terminology Criteria for Adverse Events (CTCAE) version 5.0).

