10.4 Study duration

The maximum duration of treatment for this study is planned to be a total of 36 cycles (12 cycles of tafasitamab plus lenalidomide induction, 24 cycles of tafasitamab maintenance), not to exceed 36 months.

After discontinuation of both study drugs, patients will complete an EOT visit within 7 days from the date of official treatment discontinuation. If treatment must be discontinued due to prolonged interruption for toxicity (see 10.5.7), the EOT visit will occur within 7 days of the decision to permanently discontinue treatment.

All patients will be followed for adverse events for at least 30 days following the last dose of study treatment or until initiation of new therapy, whichever comes first. Patients who proceed to tafasitamab maintenance will be followed for disease status updates for up to three years. After completing study treatment, survival, relapse, and new anti-lymphoma therapy information will be collected via telephone calls, patient medical records, and/or clinic visits approximately every 6 months until death, loss to follow up or consent withdrawal, whichever comes first.

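### Section 13.2 counts removals without progression or death as PFS events, contrary to the PFS definition in 2.2.3 and 14.0

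*Combined protocol and SAP*

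**What the plan says.** PFS is a secondary endpoint. Section 2.2.3 gives it as "defined as the time from initiation of study treatment to the earlier of POD or death from any cause". The Methods in 14.0 agree: "PFS will be defined as the time from initiation of study treatment to the earlier of POD or death from any cause". They plan Kaplan-Meier estimates with 95% confidence intervals and state no censoring rule for PFS.

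Section 13.2, in the paragraph that sets the primary analysis, adds a rule for patients who have had at least one dose of each drug. Those removed for any reason other than progression "will be counted as a failure for ORR analysis and as an event for PFS analysis". The next sentence covers OS: patients "removed from the study for any reason other than death will be censored at the time of study removal".

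Section 12.0 lists the grounds on which a patient may be removed. Besides progression and death, they include patient request, non-compliance, unacceptable toxicity, loss to follow-up, pregnancy and "Start of any other antineoplastic therapy".

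On follow-up, 10.4 states: "After completing study treatment, survival, relapse, and new anti-lymphoma therapy information will be collected via telephone calls". Medical records and clinic visits are the other routes. Contact is about every 6 months until death, loss to follow-up or withdrawal of consent.

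PFS is used again in two exploratory analyses in 14.0: "For assessing association between minimal MRD and PFS, the log rank test will be used", and genomic alterations are related to "time-to-event outcomes PFS and OS, Cox regression will be used".

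On duration of response (DOR), 2.2.2 ends it at POD, whereas 14.0 ends it at POD or death.

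**The concern.** A censoring rule would complete the PFS definition. Section 13.2 instead adds a new kind of event. Section 14.0 neither repeats this rule nor refers to it, so two statisticians working from different sections would produce different Kaplan-Meier curves, both labelled PFS.

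The composite in 13.2 is a legitimate endpoint, but it is time to treatment failure. It mixes progression and death with tolerability and administrative exits. A patient removed for toxicity without progression would have a PFS event under 13.2, yet no event for time to progression under 14.0, which needs POD or death from lymphoma.

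At stake are the reported PFS and its comparison with other post-BTKi results, and the MRD and genomic associations, where exits unrelated to disease would count as outcome events.

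**Working it through.** **1. The plan's own figures.** The documents state no PFS figure. The stated design figures rest on ORR alone: 19 then 39 patients, stop at 6 or fewer responses, promising at 17 or more. The exact calculation sums P(X1 = x) × P(X2 ≥ 17 − x) over x = 7 to 19, with X1 binomial on 19 and X2 binomial on 20. It gives 0.0455 at ORR 30% and 0.8036 at ORR 50%, in line with the stated 5% and 80%. No PFS rule enters this calculation.

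**2. The rules side by side** (patients with at least one dose of each drug).

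| First exit | PFS in 2.2.3 and 14.0 | PFS in 13.2 | OS in 13.2 |
|---|---|---|---|
| POD | event | event | censored if removed |
| Death | event | event | event |
| Removal with neither | not an event | event | censored at removal |

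The conflict lies in the third row only.

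**3. Possible size, under assumptions.** Let m be the true PFS median, λ = ln 2 / m, and h a constant removal rate independent of progression and death, with removals dated at removal. All values of m and h are assumed.

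- Median under 13.2 = ln 2 / (λ + h).
- Expected patients of 39 counted as events by month 12 only through removal = 39 × h/(λ + h) × (1 − exp(−12(λ + h))).

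Example with m = 6 and h = 0.02: λ = 0.1155, so the median is 0.6931/0.1355 = 5.1 months. The expected number is 39 × 0.1476 × (1 − exp(−1.626)) = 4.6.

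| m (months) | Median under 13.2 at h = 1%, 2%, 4% per month | Patients of 39 |
|---|---|---|
| 3 | 2.9, 2.8, 2.6 | 1.5, 3.0, 5.5 |
| 6 | 5.5, 5.1, 4.5 | 2.4, 4.6, 8.5 |
| 10 | 8.7, 7.8, 6.3 | 3.0, 5.7, 10.4 |

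Equivalently, if a share f of first exits are such removals, the median is multiplied by (1 − f). In the example f = 0.02/0.1355 = 0.148, and 6 × 0.852 = 5.1.

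**4. If removal is informative.** Suppose the hazard of POD or death becomes kλ after removal. Fully followed PFS is then S(t) = exp(−(λ+h)t) + h[exp(−(λ+h)t) − exp(−kλt)]/(kλ − λ − h). With m = 6, h = 0.02 and k = 3 (assumed), S(t) = 0.5 at t = 5.6 months. Section 13.2 gives 5.1 and censoring at removal gives 6.0, so the two are about equally far off.

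**5. Whether the estimated curves are ordered.** Take four patients: A is removed at month 2 and has POD at month 10; B has POD at month 5; C is censored at data cutoff at month 7; D is event-free to month 12.

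- Under 13.2: 3/4 × 2/3 = 0.500 from month 5 to month 12.
- Fully followed: 3/4 × 1/2 = 0.375 from month 10.

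The 13.2 estimate is the higher one from month 10.

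**The case against.** The best defence is that 13.2 is a deliberate, prespecified conservative rule that fills the gap left by 14.0, and that censoring removed patients is no safer. Part of this stands. Censoring can bias PFS upward when removal is informative, and step 4 shows it missing by about as much as 13.2. The case for change is therefore agreement with the endpoint the protocol defines twice, not lower bias in every setting. A conservative composite should carry its own name.

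The reach of the rule may also be small. The grounds in 12.0 are permissive, and 10.4 ends follow-up only at death, loss or withdrawal of consent. If removal means leaving follow-up rather than stopping treatment, few patients would be affected. That objection stands as to size, but the text does not say which meaning applies.

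A reader might infer two stronger points that the documents do not support:

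- **That the 13.2 curve must lie at or below true PFS throughout.** This holds for the underlying curves under the assumptions of step 3. Step 5 shows that it need not hold for Kaplan-Meier estimates when other patients are censored at cutoff, which accrual over 2 to 3 years makes likely.
- **That 13.2 contradicts itself by counting patients as PFS events while censoring them for OS.** The two rules cover overlapping groups, not the same one: the PFS rule excludes removals for progression and the OS rule excludes deaths. Different handling by endpoint is not in itself an error.

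**Conclusion.** The contradiction is real and should be corrected. As written, 13.2 turns the primary analysis of PFS into time to treatment failure, against 2.2.3 and 14.0. Under independent removal the underlying PFS is understated. The assumed cases run from a negligible shift (3.0 to 2.9 months) to a large one (10 to 6.3 months). These are illustrations only: the documents give no removal rate and no expected PFS, and the number of patients affected turns on the undefined meaning of removal.

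It would be wrong to infer that the trial's decision is at risk. PFS is secondary, in a single arm and without a decision threshold, and the PFS clause has no bearing on ORR, the Simon boundaries or the sample size. The DOR mismatch between 2.2.2 and 14.0 is also real, but minor.

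**What to change.** - **13.2, PFS.** Delete the part of the sentence that makes removals PFS events; the ORR part is not at issue here. Use the 2.2.3/14.0 definition throughout: the event is POD or death from any cause whenever documented, including in 10.4 follow-up. Patients without an event are censored at the last adequate disease assessment. State the rule in 14.0 as well.
- **Separate analysis.** Report the removal-as-event version beside PFS, labelled time to treatment failure and dated at removal.
- **10.4.** State that patients who stop treatment stay in follow-up unless they withdraw consent or are lost.
- **13.2, OS.** Censor at the date last known alive instead of at removal. Otherwise a patient removed at month 3 who dies at month 8 would have a PFS death event at month 8 but be censored for OS at month 3.
- **2.2.2 (minor).** End DOR at POD or death, as in 14.0.

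The cost is protocol wording, plus the contacts that 10.4 already describes for any removed patients who would otherwise not have been followed. The downside is that informative removal can bias the censored PFS upward. The time-to-treatment-failure analysis helps to show how much that could matter.
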